##### Exclusion Criteria

1. None.

#### **6.1.1.2. User Sample Size**

As per the United States Food and Drug Administration (U.S. FDA) document titled ‘Applying Human Factors and Usability Engineering to Medical Devices: Guidance for Industry and Food and Drug Administration Staff’; February 3, 2016, Section 8.1.1 Test Participants (Users), the minimum number of 15 subjects is required to be enrolled in and complete this study. The minimum sample size of 15 subjects is applicable as the intended actual user population in this validation study is a homogenous group of adults who are applicably qualified/licensed/certified/

accredited employees at cosmetology-related facilities such as nail salons, beauty salons and/or spas, fitness and wellness centers, or the like.

#### **6.1.1.3. User Sample Recruitment**

The subject user sample will be recruited from nail salons, beauty salons and/or spas, fitness and wellness centers, or the like, in the geographical area within the vicinity of the test location.

A potential candidate who voluntarily signs the informed consent form and subsequently satisfies the enrollment criteria will be enrolled as a User in this Human Factors Validation Testing study.

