### 4.1. STUDY DESIGN ELEMENTS

The key elements of the study design that support its ability to generalize study results to the intended user under intended use conditions are the following:

- (i) Users (test participants) will represent the intended (actual) users of the LunulaLaser™ OTC; that is, users will be employees at nail salons, beauty salons and spas, fitness and wellness centers, and the like;
- (ii) All critical tasks will be performed, observed and evaluated during the testing;
- (iii) The device user interface and all associated instructional/informational materials will represent the final intended post-clearance (actual use) design; and
- (iv) The simulated-use test conditions will be sufficiently realistic to represent the actual intended conditions of use. Under actual intended conditions of use, the user will receive the Erchonia LunulaLaser™ OTC device in its full packaging via delivery to the facility at which they are employed and will need to rely on the information/instructional information contained in the Installation and Proper Use Reference Guide and the device and packaging labeling to configure and operate the device for use.

(v) In this study, the user will simply be presented with the device in its intended packaging as if receiving it at their place of employment. No additional information, instruction or training will be provided by the Study Observer, or any other individual associated with the study. The user will be left to work out how to operate the Erchonia LunulaLaser™ OTC as independently and naturally as possible without interference or influence from the Study Observer. While the user will have received the instructional information in the packaging as in intended use, he or she will not be instructed to use any of the information. It will be up to the user as to if or how he or she chooses to use that information to set up operation of the device as would occur under actual conditions of intended use.

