## 6. STUDY PARTICIPANT AND ENVIRONMENTAL DESIGN

### 6.1. SUBJECTS (USERS and CLIENTS)

#### 6.1.1. USER SAMPLE

The study user sample will be representative of the population of intended users of the device who are employees at nail salons, beauty salons and spas, fitness and wellness centers, and the like.

In defining the device user and the potential impact of the device user characteristics on the user's ability to safely, and effectively, use the device, the following personal characteristics were considered and evaluated, with the outcome as follows:

Device User Characteristic	Outcome of Consideration
Physical size, strength, and stamina	Able to lift and carry 23lbs / 10.43 kg
Physical dexterity, flexibility, and coordination	Able to plug the power cord into the device and an electrical outlet; operate the key to turn the device on and off; open and close the magnetic door/foot platform using the knobs; operate the touchscreen; and correctly place the safety glasses on themselves and the client.

Sensory abilities such as vision, hearing, and tactile sensitivity	Able to read the information on the device screen display.
Cognitive abilities, including memory	Able to understand the instructions in the Installation and Proper Use Reference Guide for safe and effective use of the device; able to understand when to use the device and how to confirm client eligibility.
Medical condition for which the device is being used	n/a
Comorbidities	n/a
Literacy and language skills	English language; 5 th Grade literacy skills.
General health status	n/a
Mental and emotional state	Sufficient stability.
Relevant level of education and health literacy	Able to read at 5 th Grade level; aware of client eligibility criteria.
General knowledge of similar types of devices	Not necessary but beneficial.
Knowledge of and experience with the particular device	n/a
Ability to learn and adapt to a new device	Sufficient ability.
Willingness and motivation to learn to use a new device	Sufficient willingness and motivation.

In considering these specific characteristics of intended device users that may affect their interactions with the device, given the typical profile of the intended users of the LunulaLaser™ OTC, it was determined that there did not need to be specific evaluation of potential users within any of these specific device user categories.

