##### Inclusion Criteria

1. 18 years or older.
2. Male or female.
3. Currently employed at a nail salon, beauty salon and/or spa, fitness and wellness centers, or the like.
4. In possession of qualification(s), current licensure(s), certification(s), and/or accreditation(s), as applicable, to perform their designated tasks at their place of employment, e.g., cosmetology degree, nail technician, esthetician, massage therapist, etc.
5. Voluntarily signed consent form.

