### **7.2.3. PROVISION OF STUDY DEVICE**

The user is provided with the Erchonia LunulaLaser™ OTC in its intended packaging that also contains the Installation and Proper Use Reference Guide exactly as is intended to be supplied following FDA market clearance. The user is instructed to open the packaging and prepare the device for use exactly as they would if they were to receive it at their place of employment.

**N.B.:** There will be no participant training in preparation or use of the device in this Human Factors Validation Testing study as it is not intended that users receive any training once the device has market clearance. It is intended that the user will receive delivery of the device in its packaging at

the place of employment. The user will need to set-up and operate the device based upon the information provided with the packaging, and therefore, this Human Factors Validation Testing study will also not implement user training to optimally simulate intended use of the Erchonia LunulaLaser™ OTC in real life. Additionally, users will be left to work out how to operate the Erchonia LunulaLaser™ OTC and to administer a treatment as independently and naturally as possible, without interference, influence, or instruction from the Study Observer, including whether or not the user chooses to read the instructional materials provided including the Installation and Proper Use Reference Guide.

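### The protocol body does not guard against later users being briefed by co-workers tested earlier, although the test assumes that each user meets the device with only the package

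*Combined protocol and SAP*

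**What the plan says.** **The premise.** Section 4.1(v) has the user handed the packaged device as if it had been delivered to the workplace, and adds: "No additional information, instruction or training will be provided by the Study Observer, or any other individual associated with the study". Section 7.2.3 repeats this ("There will be no participant training in preparation or use of the device") and gives the reason: no training is intended once the device is on the market. Section 7.2.4 again tells the user to act as though the device had just arrived.

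**Who may enter.** Section 6.1.1.3 recruits from salons, spas, fitness centers and similar places "in the geographical area within the vicinity of the test location". It states no number of facilities and no limit per facility. It then says: "A potential candidate who voluntarily signs the informed consent form and subsequently satisfies the enrollment criteria will be enrolled as a User". The employment criterion is "Currently employed at a nail salon, beauty salon and/or spa, fitness and wellness centers, or the like", which co-workers meet equally. The exclusion criteria in 6.1.1.1 are None. In the user-characteristics table of 6.1.1, the row "Knowledge of and experience with the particular device" is marked n/a.

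**How many.** Section 6.1.1.2 states that "the minimum number of 15 subjects is required to be enrolled in and complete this study", citing a guidance minimum and a homogeneous user group. It gives no detection target.

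**What a user knows at the end.** By the close of 7.2.6 a user has unpacked and operated the device, been debriefed, been asked to read the whole guide and all labeling, and answered questions on them. Participation then ends. The section contains no request to keep the session private.

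**The concern.** The plan closes two routes by which help could reach a user. The observer gives no guidance and answers no questions (7.2.4), and the acting client is told to offer no insight or feedback (6.1.2). The bar in 4.1(v) covers people associated with the study in general, but it is written about what the study provides. It does not deal with a colleague who has finished a session and goes back to the same workplace. Such a colleague knows the set-up sequence, the role of the key and the safety glasses, and what the observer asks about.

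The study exists to find use difficulties, errors and close calls (2.1(iii)). Root-cause analysis and any change to the device or labeling (11.2.1, 11.2.2) can act only on what is seen. An error that a briefed user avoids is never recorded. If neither facility nor prior exposure is on file, nobody can later tell whether a clean record reflects the interface or the conversation.

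There is a second, smaller effect. Even without briefing, co-workers may share habits and experience with equipment, so 15 users from a few facilities may carry less information than 15 unrelated users.

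**Working it through.** **The plan's figure.** The 15 comes from a cited guidance minimum. It has no stated error rate, power or detection probability, so there is nothing to reproduce. What can be computed is what 15 users deliver and how that changes.

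**Inputs.** From the documents: n = 15 (6.1.1.2). Assumed, because the documents give none of them: the error rate p of an uninformed user (10%, with 20% as a check); 3 facilities of 5 users or 5 facilities of 3; the fraction r by which briefing cuts the error rate; and the intra-facility correlation (ICC).

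**Step 1: 15 independent, uninformed users.** The chance of seeing the error at least once is 1 − (1 − p)^15.
- p = 0.10: 1 − 0.9^15 = 0.794.
- p = 0.20: 1 − 0.8^15 = 0.965.

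**Step 2: briefing.** Let k users, the first from each facility, be unbriefed, and let the other 15 − k have rate p(1 − r). Detection is 1 − (1 − p)^k × (1 − p(1 − r))^(15 − k). For example, with p = 0.10 and r = 0.5:
- k = 5: 1 − 0.9^5 × 0.95^10 = 1 − 0.5905 × 0.5987 = 0.646.
- k = 3: 1 − 0.9^3 × 0.95^12 = 1 − 0.7290 × 0.5404 = 0.606.

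| Cut in error rate | 5 facilities, p = 0.10 | 3 facilities, p = 0.10 | 5 facilities, p = 0.20 | 3 facilities, p = 0.20 |
|---|---|---|---|---|
| none | 79% | 79% | 96% | 96% |
| 50% | 65% | 61% | 89% | 86% |
| 80% | 52% | 43% | 78% | 69% |
| 100% | 41% | 27% | 67% | 49% |

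The last row requires every later co-worker to have been told about that particular error and never to make it.

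**Step 3: clustering without briefing.** Under a beta-binomial model with a = p(1 − ICC)/ICC and b = (1 − p)(1 − ICC)/ICC, the chance that none of m co-workers makes the error is the product of (b + i)/(a + b + i) for i = 0 to m − 1. With p = 0.10 and ICC = 0.2, a = 0.4 and b = 3.6.
- m = 3: 0.9000 × 0.9200 × 0.9333 = 0.7728. Over 5 facilities, detection is 1 − 0.7728^5 = 0.724.
- m = 5: 0.7728 × 0.9429 × 0.9500 = 0.6922. Over 3 facilities, detection is 1 − 0.6922^3 = 0.668.

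These equal ln(0.2756)/ln(0.9) = 12.2 and ln(0.3317)/ln(0.9) = 10.5 independent users. The usual variance design effect for 3 facilities of 5 is 1 + 4 × 0.2 = 1.8, or 15/1.8 = 8.3 users. That figure describes the precision of a proportion. It overstates the loss for the question asked here, which is whether an error is seen at all. Over ICC 0.1 to 0.5, beta-binomial detection at p = 0.10 runs from 73% to 51% for 3 facilities of 5, and from 76% to 61% for 5 of 3.

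**The case against.** The strongest reply is that the mechanism is conjecture. No passage shows users talking to one another. Section 7.2.1 mentions sequential enrollment only to number subject IDs. Co-workers tested on one day without meeting between sessions would fit the text just as well. A request for silence would usually sit in the consent form (Appendix H), and an exposure question in the eligibility or debriefing forms (Appendices D and F). None of these was available to read, so they cannot be called silent. All of this stands. What remains is that the protocol body gives no such rule and that its exclusion list, which can be read, is None.

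It is also fair to say that nothing formal fails. Section 11.1 is a pass or fail for each user, with no interval, test or threshold, and the knowledge questions are little affected because everyone is asked to read the guide first. That limits the harm to error detection and generalizability.

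A third reply is that salon staff brief each other in real life. But the protocol defines its own scenario as first receipt with the package alone, and a briefed user does not test that scenario.

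A reader might infer more: that the users will not be untrained, that all 15 will come from one or two salons, or that the sample is really worth about 8. The documents do not support these. Training by the study is plainly barred. Section 6.1.1.3 names several facility types in the plural, although it sets no minimum. The figure of 8 answers a question about variance, under an assumed correlation.

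**Conclusion.** The concern holds as a gap in safeguards, not as a demonstrated flaw in the sample. Following the visible rules as written, a candidate whose colleague has already described the device and the session would be enrolled and counted as uninformed.

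The size cannot be derived from the documents. On the assumptions above, a moderate case (10% error rate, later co-workers' rate halved) lowers the chance of seeing the error from 79% to about 61–65%, and from 96% to 86–89% at a 20% rate. Clustering alone at ICC 0.2 gives 67–72% at the 10% rate. The 27–41% range is the extreme of complete suppression and should not be quoted as the expected loss. Nothing here shows that 15 is the wrong number. If Appendices D, F or H already contain an exposure question or a non-discussion request, the concern shrinks accordingly. This is a cheap improvement worth making before enrollment, because the leak can be neither measured nor repaired afterwards.

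**What to change.** 1. In 6.1.1.1, replace None with an exclusion for anyone who has used the device, or who has had the device or this test described to them. Ask about this at the eligibility evaluation (7.2.2), and change Appendix D to match.
2. In 7.2.6, ask each user on completion not to discuss the session until enrollment closes. Add this to Appendix H if needed.
3. Record a coded facility number and the test order for each user, and report observed errors by both.
4. Where practical, spread recruitment over several facilities, or test co-workers on the same day without contact between sessions. A strict limit of one user per facility is not required; it could mean approaching up to 15 employers.

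Cost: small wording changes in the protocol and forms, one extra question, two extra data fields, and possibly a few candidates screened out.

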#### **6.1.1.4. User Compensation**

The user will receive \$100 as compensation for participation in this Human Factors Validation study.

### **6.1.2. CLIENT SAMPLE**

The client sample will be employees of the study sponsor, Erchonia Corporation, who are not involved with the operation of the LunulaLaser OTC, acting as representative clients of the user sample. The acting treatment recipient will be instructed to not provide any insight or feedback during their participation, as if they were an actual client of the user.

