## 4. STUDY DESIGN

This study is an uncontrolled simulated-use human factors validation testing design to assess the intended user's ability to correctly, safely, and effectively set-up, activate and operate the LunulaLaser™ OTC, to administer a treatment to a client, and to understand the information contained in the Erchonia LunulaLaser™ OTC Installation and Proper Use Reference Guide and box labeling.

The study design is comprehensive in scope and conducted in a manner such that the results will be able to be generalized to the actual intended user and under intended conditions of actual use and be adequately sensitive to capture use errors arising from either the user interface design and/or the instructional and informative materials. Study data will be collected in a manner that will facilitate analysis of the root causes of use errors or problems during the testing.

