#### **6.1.2.1. Client Sample Recruitment**

Representative clients will be recruited from amongst employees of the study sponsor, Erchonia Corporation, who are not involved with the operation of the LunulaLaser OTC.

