### 6.3. DEVICE USER INTERFACE

The device user interface is defined as all points of interaction between the user and the device, including all elements of the device with which the user interacts (i.e., those parts of the device that users see, hear, touch). This includes all sources of information transmitted by the device (including packaging, labeling), training and all physical controls and display elements (including alarms and the logic of operation of each device component and of the user interface system as a whole).

The Erchonia LunulaLaser™ OTC device user interface includes all points of interaction between the user and the device, including all elements and components of the device and its operation with which the user interacts.

The Erchonia LunulaLaser™ OTC device user interface **components and accessories** are the following:

1. LunulaLaser™ OTC Device
2. Power cord
3. 1 client safety glasses
4. 2 Keys
5. Sani-Cloth Germicidal Wipe (Sample pack)
6. Installation and Proper Use Reference Guide

The device user interface includes the following **controls, visual displays, and visual alarms and alerts**:

1. Touch Screen that displays the:
  - Power Indicator Light
  - Start Screen and related icons, Mode Screen and related icons, including Start, Stop, Pause, and Resume icons and Time Remaining icons.
  - Device Information Screen containing device and manufacturer information.
2. Pull Knobs/Stops
3. Door/Foot Platform
4. Key Switch
5. Diode Light Indicator

6. Magnetic Latch
7. Handle
8. Power Inlet/Fuse Holder

The device user interface includes the following **labeling**:

1. Installation and Proper Use Reference Guide
2. Box Labeling
3. Device Labelling

The device user interface is used by the device user under the following **conditions and sequence of operations**:

1. During initial setup of the device, including opening and unpacking the delivery box components.
2. During establishment of an appropriate device use environment.
3. During preparation and operation of the device, including plugging the electrical cord into the device and an electrical outlet, using the key to power the device on, opening the door/foot platform, using the touchscreen to initiate and manage treatment administration, ensuring correct fitting of the safety glasses to the client, ensuring correct placement of the subject's treatment foot in the device, and using the key to power the device off.

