Safety Glasses	
The LUNULALASER™ OTC is classified by the FDA/IEC as a Class 2 laser device. This represents a current standard for use to ensure the safety of the client. A Class 2 laser is determined to have a chronic viewing hazard. Pointing the laser beam directly into the eye and maintaining it there for an extended period of time could prove to be damaging. To ensure there is no possible instance of residual effect, a pair of specialty safety glasses for use by the client during treatment is provided in the device packaging. The safety glasses, sufficiently and effectively block the laser light spectrum at OD 2+ @ 635nm, OD 0.75 @ 405nm VLT60.
 
Additionally, the following warning is included in the Installation and Proper Use Reference Guide:
 
 WARNING: The client should always be correctly fitted with the safety glasses provided before turning on the laser and doing any treatment.
 
Furthermore, Step 6 of the LunulaLaser™ OTC Treatment Protocol on page 17 of the Installation and Proper Use Reference Guide reads as follows: "Have your client put on the safety glasses..."

Logic of the overall user-system interaction, including how, when, and in what form information (i.e., feedback) is provided to the user.	
Set-up and use of the Erchonia LunulaLaser™ OTC device is designed to be inherently logical and sequential. Information, including visual confirmation via text and lights of user tasks performed are provided in real-time on the LCD and touch screen. These operations and interactions have also been designed with consideration of the design of comparable devices presently on the market.

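### Acting clients need not be naive to the device and are not told to wait for direction, so an experienced client could mask a user's omission of eyewear fitting or foot placement

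*Combined protocol and SAP*

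**What the plan says.** All references are to the combined protocol and SAP.

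- **Who may be a client.** Section 6.1.2 takes clients from "employees of the study sponsor, Erchonia Corporation, who are not involved with the operation of the LunulaLaser OTC". Section 6.1.2.1 on recruitment repeats this and adds no further condition. Section 7.2.2 describes an eligibility evaluation for users only, and no listed appendix is titled as a client form or script.
- **How the client must behave.** Section 6.1.2 says the acting recipient will be "instructed to not provide any insight or feedback during their participation, as if they were an actual client of the user".
- **What the user must do through the client.** The sequence of operations in Section 6.3 includes "ensuring correct fitting of the safety glasses to the client, ensuring correct placement of the subject's treatment foot in the device".
- **Who puts on the glasses.** The user-characteristics table in Section 6.1.1 expects the user to be able to place the glasses on the client. The Guide step cited in the Safety Glasses row of Section 6.3 reads "Have your client put on the safety glasses".
- **What the design claims.** Section 4 says the study will "be adequately sensitive to capture use errors arising from either the user interface design and/or the instructional and informative materials".
- **Size and outcome.** Section 6.1.1.2 sets a minimum of 15 users. Section 11.1 classes each user as pass or fail according to whether setup and treatment were both completed satisfactorily.

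**The concern.** Most steps in this test are done by the user alone. Eyewear and foot placement are different because they end with something done to, or by, the client. The user's part is to prompt, fit, position and check. If the client picks up the glasses unasked, or sets the foot correctly because of an earlier session, the step is complete although the user ensured nothing.

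The error at risk of being hidden is an omission. Section 5.1 counts a task not performed at all alongside one performed incorrectly. Eyewear has a safety role by the plan's own account: Section 6.3 describes a chronic viewing hazard and cites a Guide warning that the client be fitted before the laser is turned on. Foot placement is the clearer example of the two, because for eyewear the cited Guide step already gives the client a part to play.

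The eligibility rule does little to prevent this. Someone at a laser company may know eyewear practice without being involved in operating this device, and anyone who acts as client a second time has seen the procedure. What is at stake is the sensitivity to use errors that Section 4 claims.

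**Working it through.** **1. What the client rules cover.**

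| Route by which a client could complete a step | Rule in the plan |
|---|---|
| Is involved in operating this device | Excluded (6.1.2, 6.1.2.1) |
| Knows the Guide or similar sponsor lasers | Not addressed |
| Has been client in an earlier session | Not addressed; number of clients not given |
| Gives insight or feedback | Barred (6.1.2) |
| Dons glasses or places foot before being directed | Not expressly addressed; the actual-client clause bears on it |

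**2. How many sessions could have an exposed client.** The input is the minimum of 15 users (6.1.1.2). The number of clients, k, is not stated and is assumed here. If each client serves at least once, sessions with a previously exposed client = 15 − k.

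- k = 1: 15 − 1 = 14 (93%)
- k = 3: 15 − 3 = 12 (80%)
- k = 5: 15 − 5 = 10 (67%)
- k = 15: 0

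The plan permits any of these. They count exposure, not masking.

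**3. Effect on the chance of seeing an omission.** The plan gives no error rate or detection probability, so there is no figure to reproduce. Let p be the proportion of users who would omit the step and m the share of omissions hidden by the client. Both are assumptions. With independent users,

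P(at least one omission seen in 15) = 1 − (1 − p(1 − m))^15.

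| p | m = 0 | m = 0.25 | m = 0.50 | m = 0.75 |
|---|---|---|---|---|
| 0.05 | 53.7% | 43.6% | 31.6% | 17.2% |
| 0.10 | 79.4% | 68.9% | 53.7% | 31.6% |
| 0.20 | 96.5% | 91.3% | 79.4% | 53.7% |

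For example, at p = 0.20 the chance of seeing none is 0.80^15 = 3.5% with no masking and 0.90^15 = 20.6% with half masked. The table shows how far a test of 15 users depends on m. It does not say what m is.

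**The case against.** The case on the other side has real force.

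- **The conduct rule is more than a bar on speech.** Insight need not be verbal, and the instruction to behave as an actual client bears on unprompted expert behaviour. This stands. But the clause does not say what to do with the glasses or foot, and an employee cannot unlearn an earlier session.
- **The observer may see it happen.** A reader might infer that steps are scored on the end state, so that a client's action passes as the user's. The documents do not say so. Sections 6.4 and 7.2.4 have the Study Observer watch the user's performance throughout, and Section 6.3 words both tasks as the user ensuring something. The contents of Appendices A and E are not in the text available, so a rule on who initiated a step may already exist.
- **Later layers may recover it.** Debriefing asks about each critical task (6.4, 7.1). That helps, though a user who saw the step completed may report no difficulty. The knowledge evaluation follows a requested reading of the Guide (7.2.6), so it is weak evidence of what was omitted in use.
- **The route is narrow.** The user unpacks the glasses and opens the foot platform first, and a client who dons the glasses when prompted is following the Guide. Only unprompted action can mask an omission.
- **The direction is not assured.** A reader might infer that the bias can only inflate passes. Repeat clients would also learn from untrained users, who may err, so this is not established.

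**Conclusion.** The gap is real and modest. The client rules leave prior exposure and unprompted physical action open, and two user tasks are completed through the client. Masking is therefore possible while the rules as written are obeyed. The only size that follows from the plan's own numbers is exposure: between 0 and 14 of 15 sessions, depending on a number of clients that is not stated. The detection figures rest on assumed omission and masking rates and are not estimates.

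A reader might go further and conclude that clients will do these steps for the user, or that Study Passes will be inflated. The documents support neither. They allow such behaviour without predicting it, they do not state end-state scoring, and Section 11.1 sets no pass-rate threshold for an inflated count to cross. This is an inexpensive improvement to the design, not a defect that invalidates the test.

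**What to change.** 1. In Sections 6.1.2 and 6.1.2.1, require clients who have not operated, demonstrated or been trained on this or similar sponsor lasers.
2. Use a different client for each session where the number of employees allows. Otherwise record the client's session number.
3. Add to the client instruction that the client does not handle the glasses or place the foot until the user directs it. Leave the Study Observer's existing power to intervene for safety unchanged.
4. On the Appendix E form, record whether user or client initiated eyewear and foot placement, and count a client-initiated step as not performed by the user, unless the form already does this.
5. Reconcile the user-characteristics table in Section 6.1.1 with the Guide step cited in Section 6.3 on who places the glasses, so that the observer knows which user action to look for.

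The cost is a short client instruction, one or two form fields and a slightly narrower pool of employees. There may be somewhat more safety interventions. No extra users or staff are needed, unless a new client for every session strains the pool, in which case the session record serves instead.
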